4. PATIENT POPULATION

4.1 Physicians-investigators

The present study is non-interventional (an observational, multicenter, descriptive study). Randomly selected polyclinic institutions of Moscow will take part in the study and enrol into the registry 2000 COPD patients.

The patient population includes male and female patients over 40 years of age, smokers or ex-smokers, under outpatient surveillance at polyclinic institutions of Moscow with diagnosis codes according to ICD J40 - J44 and diagnosed COPD, as confirmed by spirometry results.

4.2 Selection criteria for COPD patients

4.2.1 Inclusion criteria for patients with diagnosed COPD

1. Male and female patients \geq 40 years, smokers or ex-smokers, with previously diagnosed COPD
2. COPD diagnosis corresponding to ICD codes J40 - J44 (J40 - Bronchitis, not specified as acute or chronic, J41 - Simple and mucopurulent chronic bronchitis, J41.0 - Simple chronic bronchitis, J41.8 - Mixed simple and mucopurulent chronic bronchitis, J 42 - Unspecified chronic bronchitis, J 43 - Emphysema, J 44 - Other chronic obstructive pulmonary disease)
3. COPD diagnosis confirmed by spirometry results (spirometry is performed as normal with bronchodilator testing using salbutamol 400 μ g, post-BD $FEV_1 \backslash FVC < 0.7$)

Spirometric diagnosis of disease severity should be made in line with COPD assessment according to GOLD criteria.

4.2.2 Exclusion criteria for patients with COPD risk factors and for patients with previously diagnosed COPD

A patient with diagnosed COPD should not meet any of the exclusion criteria. If a patient with previously diagnosed COPD meets at least one of the exclusion criteria such patient cannot be enrolled into the study.

1. Pulmonary comorbidities, such as tuberculosis, sarcoidosis

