The registry will include all patients with registered diagnoses J40 - J44 according to ICD-10 with spirometry results confirming COPD diagnosis, who are at the study start under outpatient surveillance, and also newly registered patients diagnosed with COPD (ICD-10 J40 - J44, as confirmed by spirometry results) during the conduction of the registry program at the selected polyclinic institutions of Moscow (according to ICD: J40 - Bronchitis, not specified as acute or chronic, J41 - Simple and mucopurulent chronic bronchitis, J41.0 - Simple chronic bronchitis, J41.8 - Mixed simple and mucopurulent chronic bronchitis, J 42 - Unspecified chronic bronchitis, J 43 - Emphysema, J 44 - Other chronic obstructive pulmonary disease) based on regular (yearly) retrospective analysis of patient records with data entry into a consolidated database.

It is planned to enrol into the study approximately **2000** male and female patients over 40 years of age with diagnosed COPD (as confirmed by spirometry results).

The present observational multicenter descriptive study will be conducted in the setting of routine clinical practice of outpatient polyclinic institutions. There is no hypothesis to be tested in this study.

The study will be conducted in outpatient polyclinic institutions of the primary medical care system of Moscow. Pulmonologists of the primary medical care system will be engaged as investigators. These are the physicians, whom the patients with tentative COPD diagnosis are referred to in the Russian Federation and who within the scope of their responsibilities have access to source medical records and who evaluate the quality of diagnosis and extent of treatment prescribed to COPD patients.

The present study is observational therefore it does not require a treatment regimen or directions for patient management. The patients receive medical care in line with routine practice for treatment of this disease in the Russian Federation. Patient participation in the study should not in any way affect the principles and extent of treatment received by the patient according to routine clinical practice.

Physicians-investigators will enter into the study the information (data) concerning COPD patients, both those already registered at the selected medical treatment and preventive care institution, and newly registered patients as they seek attention at the outpatient polyclinic institutions.

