The main purpose of the present study consists in collection of data concerning COPD patients who under surveillance at outpatient polyclinic institutions of Moscow using patient medical records and their medical history. This protocol does not specify any obligatory visits or examinations.

Patient data will be entered into the registry de-identified. The patients will be identified by their screening number and initials. Then the Physician-investigator will evaluate patient compliance with inclusion criteria. The study will enrol patients meeting all the inclusion criteria and not having any of the exclusion criteria.

Only the physician who enters patient data into the regional COPD registry possesses patient contact information, and henceforth only this physician will enter de-identified patient data according to study design. This physician does not influence the choice of examination extent, treatment strategy and medication.

Study variables

Primary variables

1. Description of the clinical profile of COPD patient under outpatient surveillance at polyclinic institutions of Moscow (including demographic data (age, gender, ethnicity, occupation), smoking status, disease duration, disease severity grade, distribution by disease phenotype, disease exacerbation rate in the setting of real-life clinical practice)

Secondary variables:

1. Percentage of patients with different disease phenotypes among outpatients
2. Percentage of prescriptions of medicinal products to COPD patients depending on disease severity grade in the setting of real-life clinical practice

Number/Code:
Version:
Date:

3. Distribution (%) of COPD patients who seek attention from primary medical care physicians by severity of airway obstruction (according to Federal clinical guidelines for diagnosis and treatment of COPD patients, 2014)
4. Mean number of exacerbations requiring medical attention (outpatient prescription of oral corticosteroids and/or antibiotics) in the last year in COPD patients
5. Mean number of hospitalizations in the last year in COPD patients
6. Percentage of patients with eosinophilic inflammation
7. Description of treatment regimens prescribed to COPD patients depending on disease severity grade in the setting of real-life clinical practice
8. Percentage of prescriptions for treatment of COPD patients in line with the current Federal clinical guidelines for diagnosis and treatment of chronic obstructive pulmonary disease

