2. STUDY OBJECTIVES

2.1. Primary study objective

1. To describe the clinical profile of COPD patient who is under outpatient surveillance at polyclinic institutions of Moscow (including demographic data (age, gender, ethnicity, occupation), smoking status, disease duration, disease severity grade, distribution by disease phenotype, disease exacerbation rate in the setting of real-life clinical practice)

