3. STUDY PLAN AND PROCEDURES

The registry of COPD patients represents a non-interventional multicenter descriptive retrospective study of all COPD patients, which medical records will be retrospectively added to the registry database and newly diagnosed under outpatient surveillance at the selected polyclinic institutions of Moscow with retrospective entry of data.

it will include all patients with registered diagnoses J40 - J44 according to ICD-10 with spirometry results confirming COPD diagnosis, who are at the study start under outpatient surveillance, and also newly registered patients diagnosed with COPD (ICD-10 J40 - J44, as confirmed by spirometry results) during the conduction of the registry program at the selected polyclinic institutions of Moscow (according to ICD: J40 - Bronchitis, not specified as acute or chronic, J41 - Simple and mucopurulent chronic bronchitis, J41.0 - Simple chronic bronchitis, J41.8 - Mixed simple and mucopurulent chronic bronchitis, J 42 - Unspecified chronic bronchitis, J 43 - Emphysema, J 44 - Other chronic obstructive pulmonary disease) based on regular (yearly) retrospective analysis of patient records with data entry into a consolidated database.

It is planned to enrol into the study approximately **2000** male and female patients over 40 years of age with diagnosed COPD (as confirmed by spirometry results).

The present observational multicenter descriptive study will be conducted in the setting of routine clinical practice of outpatient polyclinic institutions. There is no hypothesis to be tested in this study.

The study will be conducted in outpatient polyclinic institutions of the primary medical care system of Moscow. Pulmonologists of the primary medical care system will be engaged as investigators. These are the physicians, whom the patients with tentative COPD diagnosis are referred to in the Russian Federation and who within the scope of their responsibilities have access to source medical records and who evaluate the quality of diagnosis and extent of treatment prescribed to COPD patients.

The present study is observational therefore it does not require a treatment regimen or directions for patient management. The patients receive medical care in line with routine practice for treatment of this disease in the Russian Federation. Patient participation in the

study should not in any way affect the principles and extent of treatment received by the patient according to routine clinical practice.

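### Entry is limited to smokers and ex-smokers, but the registry description, aims and results are worded for COPD outpatients without that limit

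*Combined protocol and SAP*

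**What the plan says.** **Who may enter.** Section 4.2.1, item 1, requires "smokers or ex-smokers, with previously diagnosed COPD". Section 4.1 says the same of the population: "The patient population includes male and female patients over 40 years of age, smokers or ex-smokers, under outpatient surveillance". The synopsis (Study design) and Section 3 both state that only patients who satisfy every inclusion criterion and no exclusion criterion are enrolled. Section 5.1 allows withdrawal of a patient who was enrolled in breach.

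**Whom the registry is said to cover.** The synopsis (Study design) states: "The registry will include all patients with registered diagnoses J40 - J44 according to ICD-10 with spirometry results confirming COPD diagnosis". Section 3 repeats it: "it will include all patients with registered diagnoses J40 - J44 according to ICD-10 with spirometry results confirming COPD diagnosis". The sentence on planned enrolment that follows in both places names age, diagnosis and spirometry, but not smoking.

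**Whom the results are said to describe.** The primary objective (synopsis and Section 2.1) is "To describe the clinical profile of COPD patient who is under outpatient surveillance at polyclinic institutions of Moscow". The profile includes "demographic data (age, gender, ethnicity, occupation), smoking status, disease duration, disease severity grade". The synopsis primary variable reads "Description of the clinical profile of COPD patient under outpatient surveillance at polyclinic institutions of Moscow", and Sections 8.1 and 12.2 word the primary endpoint in the same general way. The secondary objectives, variables and endpoints (synopsis, Sections 2.2, 8.2 and 12.2) refer to COPD patients or outpatients. The synopsis rationale expects the phenotype percentages and treatment findings to be usable in other regions. None of these carries a smoking limit, and no section gives a reason for it.

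**What is recorded on smoking.** Sections 3 and 7.1 collect smoking status, with pack-years where possible.

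**The concern.** Section 3 states: "There is no hypothesis to be tested in this study". In a purely descriptive registry the product is a set of percentages and means attached to a named population, so an incorrect name makes the conclusion incorrect even if every record is accurate.

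The plan describes its population in two ways that cannot both be true: every spirometry-confirmed J40-J44 outpatient, and smokers or ex-smokers only. The smoking criterion also selects on a characteristic that the primary objective sets out to describe. If the general wording passes into the report, the smoking distribution of a group chosen for having smoked would be read as that of Moscow COPD outpatients. The phenotype, severity, eosinophil and guideline-concordance percentages would likewise be ever-smoker results under a wider label, and the expectation for other regions would extend that label further.

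**Working it through.** The plan gives no figure to reproduce: Section 12.5 says no sample size was calculated, and the documents give no share of never-smokers. The check is a comparison of texts and one piece of algebra.

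**Step 1: the texts side by side**

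- Section 4.1 and Section 4.2.1, item 1: smoking limit stated.
- Synopsis Study design and Section 3, registry description: no smoking limit; every patient with the diagnosis codes and confirming spirometry.
- Synopsis Study design and Section 3, enrolment rule: defers to the inclusion criteria, so the limit applies in practice.
- Primary objective, variable and endpoint: no smoking limit.
- Secondary objectives, variables and endpoints: no smoking limit.
- Expectation for other regions (synopsis rationale): no smoking limit.

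Several of these are the same statement repeated in synopsis and body, so the number of places adds no weight. The enrolled set is ever-smokers, and no section attaches that description to the results.

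**Step 2: effect on smoking status**

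Among otherwise eligible patients let C be current smokers, E ex-smokers and N never-smokers.

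- Current-smoker share in the registry: s = C/(C+E).
- Current-smoker share among all otherwise eligible patients: C/(C+E+N).
- With q = N/(C+E+N), the second equals s(1 − q).
- Difference: s − s(1 − q) = s·q. It is never negative, and is zero only if N = 0 or C = 0.

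The direction is therefore fixed. The documents give none of C, E or N, so the size is not.

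**Step 3: illustration only, on assumed values**

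Assume s = 50%. Both s and q are assumptions, not figures from the documents.

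- q = 5%: 50% × 0.95 = 47.5%, difference 2.5 points.
- q = 10%: 50% × 0.90 = 45%, difference 5 points.
- q = 20%: 50% × 0.80 = 40%, difference 10 points.
- q = 30%: 50% × 0.70 = 35%, difference 15 points.

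For comparison, the half-width of a 95% interval at 50% with 2000 patients is 1.96 × √(0.5 × 0.5/2000) = 2.19 points, under simple random sampling and ignoring clustering by polyclinic. With s = 50%, the difference falls inside that half-width when q is below 2.19/50 = 4.4%. The result depends entirely on q. Whatever q is, more patients would not remove the difference, and the confidence interval does not allow for it.

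**Step 4: other characteristics**

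For a characteristic with prevalence pE in ever-smokers and pN in never-smokers, the difference between the registry and all otherwise eligible patients is q(pE − pN). The documents give neither q nor the sign of pE − pN, so neither size nor direction can be stated.

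**The case against.** The limit is not hidden. It stands in the chapter on the patient population and in the formal criteria, and the design text defers to those criteria. A reader might infer that the enrolled population is undefined; the documents do not support that.

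Objectives rarely repeat eligibility rules, and the primary objective also omits the age limit, the spirometry requirement and the exclusion of tuberculosis and sarcoidosis. This stands as a general point. But the age and spirometry limits do appear in the registry description and planned-enrolment sentence of the synopsis and Section 3, whereas the smoking limit does not, and the wording there contradicts it. The tuberculosis and sarcoidosis exclusion is not in that text either, but it does not act on a named component of the primary profile. Smoking status is such a component.

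A reader might also infer that the report will present never-smokers as 0% of Moscow COPD outpatients. The documents contain no table shells and no smoking categories, so that is a prediction, not something planned. A report of current versus ex-smokers would be a natural reading of criterion 1, and the variable stays informative in that form.

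Finally, Version 3.0 is dated March 2018 and last enrolment is planned for the second quarter of 2018, so rewording would change few or no records. That is true, but analysis follows database lock (Section 12.3), planned for the fourth quarter of 2018, with the final report in the first quarter of 2019. Labels and conclusions can still be set.

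**Conclusion.** The point holds as one of consistency and labelling. The registry description conflicts with Section 4.1 and criterion 1, and no section limits the primary results, secondary results or wider use to ever-smokers. Never-smokers cannot appear in the smoking distribution, and the current-smoker share is C/(C+E), which cannot be lower than the share with otherwise eligible never-smokers counted.

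No size follows from the documents. A reader might take the illustrative 2.5 to 15 points as an estimate of bias; they rest on two assumed inputs and carry no weight in this conclusion. Nor do the documents show that phenotype, severity, eosinophil or prescribing percentages differ from those of all COPD outpatients, in either direction.

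A reader might also infer that restricting entry to ever-smokers is a design error. That is not claimed: the data can validly describe ever-smokers provided they are named as such. The conclusion assumes that criterion 1 is applied as written, as the enrolment rule and Section 5.1 indicate. The correction should be made, because it decides which population the registry speaks for and costs little.

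**What to change.** Reconcile the registry description (synopsis Study design, Section 3) with Sections 4.1 and 4.2.1.

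**If the smoking criterion stays:**

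- State that the registry population, and all primary and secondary results, describe ever-smokers (current or ex-smokers) with spirometry-confirmed COPD.
- Carry that wording in table titles, in the conclusions and in the statement on other regions.
- Report smoking status as current versus ex-smoker, with pack-years where available, and not as the smoking distribution of all COPD outpatients.

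**If every spirometry-confirmed patient is the intent:**

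- Bring the eligibility wording into line.
- Identify in the report the patients already enrolled under the restriction.

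A count of otherwise eligible never-smokers who were not enrolled is optional. The plan promises no such count, and it may be incomplete for records already reviewed.

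**Cost.** If the criterion stays, the conclusion is narrower: nothing can be said about never-smokers or about COPD outpatients as a whole. Any amended protocol wording needs written ethics approval before use (Section 10.1). Table titles and conclusions can carry the limit without an amendment, and labelling needs no new data for enrolled patients.

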5. PATIENT WITHDRAWAL FROM THE STUDY

5.1 Withdrawal criteria

A patient can be withdrawn from the study due to the following reasons:

1. A patient can be withdrawn from the study if he/she was enrolled in breach of inclusion/exclusion criteria.

5.2 Procedures for patient withdrawal from the study

In case if a patient is withdrawn from the study, he/she will continue receiving the necessary treatment in line with routine practice.

6. PATIENT TREATMENT

6.1 Treatment strategy in observational studies

This study is observational therefore it does not require a specific treatment regimen or instructions for patient management. The question of patient "assignment" to a specific treatment strategy is not predetermined by the study protocol. The patients receive medical care in line with routine practice for treatment of this disease in the Russian Federation. Patient participation in the study should not in any way affect the principles and extent of treatment received by him/her according to routine clinical practice.

7. STUDY CONDUCTION

7.1 Description of the visits

Visit "Enrolment". At this visit the patients will be enrolled into the study. De-identified data are entered retrospectively based on analysis of the outpatient medical records.

At this visit the Physician-investigator will complete the following information (collected retrospectively):

1. Verify inclusion/exclusion criteria
2. Establish the date of COPD diagnosis
3. Collect medical history concerning significant comorbidities and clinical characteristics, rate of exacerbations, pneumonia cases, hospitalizations, number of emergency calls, number of outpatient visits concerning COPD, number of days of disability in the year prior to enrolment
4. Evaluate smoking status. Wherever possible, smoking in pack-years
5. Collect medical history concerning treatment regimens, including different regimens of CS use, which the patient took/was prescribed in the year prior to enrolment into the registry (trade name of the medicinal product and INN, doses, dosing regimen, duration of use)
6. Collect demographic data and information concerning the patient's socioeconomic status
7. Collect data concerning the results of laboratory tests and instrumental examination methods confirming COPD diagnosis, present in the outpatient medical records (spirometry, specific complaints, haematology, instrumental examination methods)
8. Determine the patient's phenotype according to current classification
9. Collect data concerning adverse drug reactions
10. Complete the CRF.

8. PARAMETERS COLLECTED FOR STUDY, ASSESSMENT AND REGISTRATION METHODS

Spirometric classification of airflow limitation in COPD (refer to Appendix 2)

Spirometric classification of airflow limitation is divided into 4 stages (GOLD 1 –mild; GOLD 2 – moderate; GOLD 3 – severe; GOLD 4 – very severe), as seen in patients with $FEV_1/FVC < 0.70$, based on post-bronchodilator FEV_1 (reference to GOLD).

Assessment of exacerbations

A COPD exacerbation is defined as an acute event characterized by deterioration of respiratory symptoms outside the range of their day-to-day variations and requiring change of treatment. The rate of exacerbations substantially varies in different patients.

In the group people suffering from COPD, the number of disease exacerbations in the last year is of outstanding interest to us. A COPD exacerbation represents any deterioration in the patient's health which manifests as intensification of symptoms: worsened dyspnoea, cough, more sputum or altered sputum characteristics –purulent sputum. During exacerbations, either all of these symptoms or only some may intensify. Very often (approximately in 50% of cases) an exacerbation is associated with a viral or bacterial infection and accompanied with fever and/or respiratory infection symptoms.

8.1 Primary endpoint

1. Description of the clinical profile of COPD patient under outpatient treatment/surveillance at outpatient polyclinic healthcare institutions of the Russian Federation in Moscow.

8.2 Secondary endpoints

1. Percentage (%) of patients with different disease phenotypes among outpatients
2. Percentage (%) of prescriptions of medicinal products to COPD patients which are in line with their disease severity according to Federal clinical guidelines for diagnosis and treatment of COPD patients, 2014
3. Distribution (%) of COPD patients who seek attention from primary medical care physicians by severity of airway obstruction (according to Federal clinical guidelines for diagnosis and treatment of COPD patients, 2014)
4. Mean number of exacerbations requiring medical attention (outpatient prescription of oral corticosteroids CS and/or antibiotics) in the last year in COPD patients
5. Mean number of hospitalizations in the last year in COPD patients
6. Mean duration (seriousness) of a temporary disability case. Number of days of temporary disability /Number of cases of temporary disability (reference form 16-BH)
7. Percentage (%) of COPD patients who received different regimens for treatment of COPD, including short-acting muscarinic antagonist (SAMA), short-acting β_2 -agonists (SABA), long-acting β_2 -agonists (LABA), long-acting muscarinic antagonist (LAMA),

oral corticosteroids (oral CS), fixed dose combination (FDC), phosphodiesterase-4 inhibitor, theophylline for the past year

8. Percentage (%) prescriptions to COPD patients which are in line with their disease severity according to GOLD classification and Federal clinical guidelines for treatment choice
9. Percentage (%) of patients with eosinophilic inflammation (eosinophil count according to haematology $>2\%$, $>3\%$, $>4\%$ or equivalent to absolute counts of >200 , >300 , >400 cells per μl)
10. Percentage of patients receiving sufficient extent of treatment in line with disease severity according to Federal clinical guidelines for diagnosis and treatment of COPD patients, 2014
11. Disease burden based on the collected data concerning the duration of temporary disability, number of hospitalizations due to COPD exacerbations, outpatient visits concerning COPD during follow-up

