2.2. Secondary objectives

1. Characterize distribution (percentage (%)) of COPD patients who seek attention from primary medical care physicians by severity of airway obstruction, by reversibility of airway obstruction according to criteria described in Federal clinical guidelines for COPD diagnosis and treatment 2014
2. To determine prevalence of the different disease phenotypes among outpatients: chronic bronchitis phenotype, emphysema phenotype, mixed phenotype, frequent exacerbator phenotype, Asthma+COPD phenotype (according to criteria described in Federal clinical guidelines for COPD diagnosis and treatment 2013)
3. To determine the percentage of patients with eosinophilic inflammation according to haematology results
4. To describe treatment regimens prescribed to COPD patients depending on disease severity grade in the setting of real-life clinical practice

5. To establish the percentage of medical prescriptions for treatment of COPD patients which comply with current Federal clinical guidelines for diagnosis and treatment of chronic obstructive pulmonary disease
6. To establish prevalence and pattern of comorbidities in COPD patients
7. To evaluate the disease burden based on the collected data concerning the duration of temporary disability, number of hospitalizations due to COPD exacerbations, number of outpatient visits concerning COPD patients under outpatient surveillance at polyclinic institutions of Moscow for three years

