Physicians-investigators will enter into the study the information (data) concerning COPD patients, both those already registered at the selected medical treatment and preventive care institution, and newly registered patients as they seek attention at the outpatient polyclinic institutions during the registry conduction period.

The main purpose of the present study consists in collection of data concerning COPD patients under surveillance at outpatient polyclinic institutions of Moscow using patient medical records and their medical history. This protocol does not specify any obligatory visits or examinations.

Patient data will be entered into the registry de-identified. The patients will be identified by their screening number and initials. Then the Physician-investigator will evaluate patient compliance with inclusion criteria. The study will enrol patients meeting all the inclusion criteria and not having any of the exclusion criteria.

Only the physician who enters patient data into the regional COPD registry possesses patient contact information, and henceforth only this physician will enter de-identified patient data according to study design. This physician does not influence the choice of examination extent, treatment strategy and medication.

Visit "Enrolment". At this visit de-identified data of the patients will be included into the study. De-identified data are entered retrospectively based on analysis of the outpatient medical records.

At this visit the Physician-investigator will complete the following information (collected retrospectively):

1. Verify inclusion/ exclusion criteria
2. Establish the date of COPD diagnosis
3. Collect medical history concerning significant comorbidities and clinical characteristics, rate of exacerbations, pneumonia cases, hospitalizations, number of outpatient visits concerning COPD, number of days of disability in the year prior to enrolment
4. Evaluate smoking status. Wherever possible, smoking in pack-years
5. Collect medical history concerning treatment regimens, including different regimens of CS use, which the patient took/was prescribed in the year prior to enrolment into the registry (trade name of the medicinal product and INN, doses, dosing regimen, duration of use)
6. Collect demographic data and information concerning the patient's socioeconomic status

Number/Code:
Version:
Date:

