7. Collect data concerning the results of laboratory tests and instrumental examination methods confirming COPD diagnosis, present in the outpatient medical records (spirometry, specific complaints, haematology, instrumental examination methods)
8. Determine the patient's phenotype according to current classification
9. Collect data concerning adverse drug reactions
10. Complete the CRF.

Table 1. Visit schedule

Procedures	Visit "Enrolment"
Timelines	At the moment of enrolment into the registry
Inclusion / exclusion criteria	X
COPD. Severity grade, reversibility of airway obstruction (according to spirometry results*)	X
Demographics (year of birth, ethnicity, gender),	X
Socioeconomic status (education, occupation)	X
Smoking status	X
Occupational status, including information regarding the number of days of disability in the past 1 year.	X
Height, Weight, BMI (if applicable)	X
Comorbidities and clinical characteristics	X
Number of exacerbations COPD	X
Number of outpatient visits concerning COPD per year	X
Mean number of hospitalizations due to COPD	X
Determination of patient's phenotype according to current classification	X
Medical history concerning prior treatment of COPD	X
Medical history concerning treatment of COPD in the year prior to enrolment	X
Collection of data regarding changes in regimens of COPD treatment in the year prior to enrolment	X
Information concerning new complaints	
Spirometry. Results evolution (if applicable*)	X
Chest X-ray examination (if applicable*)	X*
Eosinophilia (eosinophil blood count based on haematology (Data of Le, EOS in % and in cells per μ l (haematology)	X
Pulse oximetry (if applicable*)	X*
Adverse drug reactions	X
CRF completion	

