12.4 Statistical methods

Descriptive statistics methods will be used for data processing.

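### The eosinophil endpoint treats >2%, >3%, >4% as equivalent to >200, >300, >400 cells/µl, which holds only at a white count of 10,000/µl, so the reported percentage may mix two rules

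*Combined protocol and SAP*

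**What the plan says.** Secondary objective 3 (section 2.2) asks for a single figure: "To determine the percentage of patients with eosinophilic inflammation according to haematology results". It names no unit and no cut-off, and neither does the corresponding variable in the synopsis. The cut-offs appear only in item 9 of section 8.2, repeated in section 12.2. There the relative thresholds of 2%, 3% and 4% are followed by "or equivalent to absolute counts of" more than 200, 300 and 400 cells/µl.

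Table 1 (section 3) lists the haematology to be taken from the records: "Data of Le, EOS in % and in cells per" µl. I read Le as leukocytes. The values come from existing outpatient records, and section 3 adds: "This protocol does not specify any obligatory visits or examinations". On analysis, section 12.4 says only: "Descriptive statistics methods will be used for data processing". Nothing in the document says which unit takes precedence, or that the two sets of thresholds will be tabulated apart.

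**The concern.** A relative and an absolute eosinophil count are tied together by the patient's white count, so no fixed pair of thresholds can be equivalent across patients. Calling them equivalent invites the analyst to treat the units as interchangeable, and the wording permits this in two ways:

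- **Reading (a):** a patient is positive if either scale is exceeded.
- **Reading (b):** a patient is classed on whichever unit the record happens to hold.

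Under (a) the percentage can never be lower than on one scale alone. Under (b) it depends on the mix of units in the records, which the documents do not give. Either way a reader could not tell which rule produced the figure. The study tests no hypothesis, so the percentages themselves are the result.

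**Working it through.** **1. Inputs from the plan.** Relative cut-offs of 2, 3 and 4%; absolute cut-offs of 200, 300 and 400 cells/µl (8.2 and 12.2, item 9). No white count is stated.

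**2. Testing the stated equivalence.** Absolute count = leukocytes × % / 100, so a pair agrees when leukocytes = absolute cut-off / (% / 100):

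- 200 / 0.02 = 10,000/µl
- 300 / 0.03 = 10,000/µl
- 400 / 0.04 = 10,000/µl

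The equivalence is reproduced at that white count and at no other:

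| White count per µl | 2 / 3 / 4% in cells/µl | 200 / 300 / 400 cells/µl in % |
|---|---|---|
| 5,000 | 100 / 150 / 200 | 4.0 / 6.0 / 8.0 |
| 7,000 | 140 / 210 / 280 | 2.9 / 4.3 / 5.7 |
| 8,000 | 160 / 240 / 320 | 2.5 / 3.75 / 5.0 |
| 10,000 | 200 / 300 / 400 | 2.0 / 3.0 / 4.0 |
| 12,000 | 240 / 360 / 480 | 1.7 / 2.5 / 3.3 |

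Below 10,000/µl the percentage rule is the looser one; above it, the absolute rule is.

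**3. Patients can be misaligned in both directions.** At 7,000/µl, 2.5% is 7,000 × 0.025 = 175 cells/µl: above 2%, not above 200. At 12,000/µl, 1.8% is 12,000 × 0.018 = 216 cells/µl: above 200, not above 2%.

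**4. Possible size (assumed distributions, none from the documents).** White count and eosinophil % are taken as independent lognormals with log-SDs of 0.25 and 0.7. In the central case the medians are 7,500/µl and 2.3%, so the median absolute count is 7,500 × 0.023 = 172.5 cells/µl, with log-SD √(0.7² + 0.25²) = 0.743.

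- Share above 2%: Φ[ln(2.3/2)/0.7] = Φ(0.200) = 57.9%
- Share above 200 cells/µl: Φ[ln(172.5/200)/0.743] = Φ(−0.199) = 42.1%
- Classed differently by the two rules: 17.4% (bivariate normal)
- Positive on either rule: (57.9 + 42.1 + 17.4)/2 = 58.7%

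At 3%/300 the shares are 35% relative, 23% absolute and 14% classed differently. At 4%/400 they are 21%, 13% and 10%.

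**5. Reading (b), central case, 2%/200.** If a share q of records is classed by percentage, unrelated to eosinophil level, the reported figure is 42 + 16q. For q = 0.25, 0.50 and 0.75 that is 46%, 50% and 54%.

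**6. Range.** Eosinophil medians of 1.8, 2.3 and 3.0%, independent of the white count; the gap is relative minus absolute:

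| Median white count per µl | Pair | Gap, points | Classed differently |
|---|---|---|---|
| 6,500–8,500 | 2%/200 | 8 to 23 | 12–24% |
| 6,500–8,500 | 3%/300 | 5 to 22 | 9–22% |
| 6,500–8,500 | 4%/400 | 3 to 17 | 6–18% |
| 10,000 | all three | about −1 to +1 | 6–11% |
| 12,000 | all three | −10 to −7 | 9–14% |

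With a correlation of −0.3 or +0.3 between the logs, and white-count medians of 6,500–8,500/µl, the three pairs span gaps of 1 to 25 points, with 5–25% classed differently.

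**7. Yardstick.** With data on all 2,000 patients, the widest 95% half-width for a percentage is 1.96 × √(0.5 × 0.5 / 2,000) = 2.2 points.

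**The case against.** The best defence accepts the arithmetic and disputes the consequence. Pooling is inferred: with six cut-offs and Table 1 asking for leukocytes and both eosinophil units, a grid of separate percentages is at least as natural an output as one pooled classification. The gap between scales is also not itself the effect of pooling, and it would remain as two different numbers after the fix. Under reading (a), with median white counts of 6,500–8,500/µl and independence, counting either scale adds only about 0.2 to 2.2 points to the relative rule, no more than sampling error. Reading (b) needs a mix of units that nobody has documented. The log-SDs are held fixed throughout, and the sign of the gap follows the assumed white-count median.

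Much of this stands. The plan permits pooling but does not say that it will happen, and the simulated sizes show only what is possible. Reading (a) is nevertheless far from the absolute rule (58.7 − 42.1 = 16.6 points in the central case), and at a median of 10,000/µl it exceeds the relative rule by about 4 to 6 points. That Table 1 allows a separate tabulation makes the repair cheap but does not supply the missing rule. If the three thresholds are meant as three separate percentages, the mismatch still affects each pair.

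**Conclusion.** The concern holds. The stated equivalence is false except at exactly 10,000 leukocytes/µl; that follows from the definition of the counts and rests on no assumption. Because the plan gives neither precedence nor separate tabulation, the reported percentage may combine two different rules.

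The size is illustrative. Under the assumed independent distributions with median white counts of 6,500–8,500/µl, the choice of rule moves the percentage by 3 to 23 points across the three pairs, which in most settings exceeds the 2.2-point sampling half-width. The gap nearly vanishes at a median of 10,000/µl and reverses at 12,000/µl, but some patients are classed differently in every setting.

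The stakes are limited: this is one of eleven descriptive secondary endpoints, and no test, sample size or primary result depends on it. It should be corrected, but it does not threaten the study.

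**What to change.** In item 9 of sections 8.2 and 12.2, remove the claim of equivalence and state that the endpoint is reported separately as (a) relative count >2%, >3%, >4% and (b) absolute count >200, >300, >400 cells/µl, and that the two sets are never combined into one classification. Add the data rules:

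- Where the absolute count is missing but leukocytes and % are recorded, derive it as leukocytes × % / 100.
- Where leukocytes are also missing, count the patient in the relative set only.
- Where only an absolute count is recorded, count the patient in the absolute set only.
- Give the number of patients with data for each set. The sets may contain different patients, so a cross-tabulation among those with both would help the reader.

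The cost is one reworded item in two places, one derived variable and a longer table, with no new data. The absolute set may be smaller, because no examination is obligatory. Section 10.1 requires written ethics approval before an amended protocol is implemented. Section 12.3 places all analysis after database lock, so data collection is unaffected.
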